5.2.3 Statistical Methods

All statistical analyses were performed with R version 4.0.2. Normally distributed continuous variables were reported as the mean \pm SD, and non-normally distributed continuous variables were expressed as the median and interquartile range. Categorical data were expressed as absolute values and percentages and analyzed using the chi-square or Fisher's exact test. The Student's t-test or Wilcoxon rank-sum test was performed to determine differences between groups. Survival analyses were based on the time to the first event. The cumulative incidence of the time-to-event end points is expressed as Kaplan-Meier curves over 24 months after randomization. Cox proportional hazard models were used to estimate HR and 2-sided 95% CI. A linear mixed-effects model was used to analyze the differences in changes of LVEF and 6MWD between the ALA group and the placebo group, with study centers included as random effects. Subgroup analysis was performed for age (whether \leq 65 years old), sex, smoking status, past medical history (hypertension, diabetes mellitus, atrial fibrillation), NYHA functional class, NT-proBNP levels, LVEF (whether \leq 30%), and whether the patient received triple therapy.

The analysis of safety and efficacy was performed in full analysis set (FAS) adhering to the intention-to-treat principle. The type I error rate (2-sided α) was set at 0.05.

六、Ethics

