3.6 Study Endpoint

3.6.1 Primary Endpoint:

A composite endpoint of all-cause death and rehospitalization due to heart failure during the 24-month follow-up period.

3.6.2 Secondary Endpoints:

The second endpoints included all-cause death and rehospitalization due to heart failure, non-fatal MI or non-fatal stroke during the 24-month follow-up period. The changes of LVEF and 6MWD were also assessed from baseline to 24 months.

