5.1 Sample Size Calculation

This pilot and feasibility study was designed to evaluate the efficacy and safety of ALA in IHF patients and get the reference data on outcomes related to clinical events for the future RCT with large sample size. As a feasibility trial, 300 patients were expected to be enrolled during the study period. Assumptions for sample size calculation included the following: the event rate for primary outcomes was 35% at 24 months in the control group[30]; the HR for the ALA group was estimated to be 0.60 and a withdrawal rate of 5% at 24 months in both groups. A total of 300 (150 per group) subjects followed up for a fixed period of 24 months provides 80% power to reject the null hypothesis at the two-sided 0.1 significance level.

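### Kaplan-Meier is fixed for the cumulative incidence of every time-to-event endpoint; for heart-failure rehospitalization, non-fatal MI and non-fatal stroke taken singly it modestly overstates the 24-month incidence, because death is a competing event

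*Protocol*

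**What the plan says.** Section 5.2.3 (Statistical Methods) names the quantity and the estimator together: "The cumulative incidence of the time-to-event end points is expressed as Kaplan-Meier curves over 24 months after randomization". It makes no exception by endpoint and mentions no competing-risk method. The same paragraph adds "Survival analyses were based on the time to the first event" and "Cox proportional hazard models were used to estimate HR and 2-sided 95% CI".

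Section 3.6.1 defines the primary endpoint as "A composite endpoint of all-cause death and rehospitalization due to heart failure during the 24-month follow-up period". Section 3.6.2 then lists the secondary events: "The second endpoints included all-cause death and rehospitalization due to heart failure, non-fatal MI or non-fatal stroke during the 24-month follow-up period". Section 3.6.3 defines death, heart-failure rehospitalization, MI and stroke separately.

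Section 5.1 gives part of the trial's purpose as to "get the reference data on outcomes related to clinical events for the future RCT with large sample size".

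**The concern.** Cumulative incidence at 24 months is the proportion of randomized patients who have had the event by then. If the event excludes death, a patient who dies first can never have it. Kaplan-Meier with censoring at death treats that patient as still at risk, with the same future hazard as the survivors. One minus Kaplan-Meier is then the risk in a hypothetical setting without death, and it exceeds the cumulative incidence whenever deaths come before the event. The bias runs in one direction and does not shrink with more patients.

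Two outputs are exposed. One is the absolute rate of each non-fatal endpoint, which belongs to the event data the trial means to pass on to a larger study. The other is the absolute difference between arms: if the two hazards are lower under ALA, the overstatement is larger under placebo and the apparent absolute benefit grows slightly.

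**Working it through.** The protocol prints no figure for these curves, so there is no stated value to reproduce. The check estimates the size of the bias from the protocol's planning figures.

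**Inputs from the protocol (section 5.1).** Control rate for the primary composite 35% at 24 months; HR 0.60; 150 patients per group.

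**Assumptions not in the protocol.** Constant hazards; HR 0.60 applying equally to death and to heart-failure admission; a share *s* of first events that are heart-failure admissions, taken as 50%, 75% and 90%; and, for MI or stroke, the 24-month mortality and the Kaplan-Meier rate.

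**Step 1: total first-event hazard over 24 months.**
- Placebo: H = -ln(1 - 0.35) = 0.4308.
- ALA: 0.60 × 0.4308 = 0.2585, so the composite rate is 1 - 0.65^0.60 = 22.8%.

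**Step 2: heart-failure rehospitalization.**
- One minus Kaplan-Meier, death censored: 1 - exp(-sH).
- True cumulative incidence (the Aalen-Johansen target): s × (1 - exp(-H)).

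Example, placebo, s = 0.50: 1 - exp(-0.2154) = 19.4%, against 0.50 × 35% = 17.5%.

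| s | Placebo: KM vs true | Excess (points) | ALA: KM vs true | Excess (points) |
|---|---|---|---|---|
| 50% | 19.4% vs 17.5% | 1.9 | 12.1% vs 11.4% | 0.7 |
| 75% | 27.6% vs 26.2% | 1.4 | 17.6% vs 17.1% | 0.5 |
| 90% | 32.1% vs 31.5% | 0.6 | 20.8% vs 20.5% | 0.3 |

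In relative terms the placebo excess is about 11%, 5% and 2%.

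**Step 3: difference between arms (placebo minus ALA).**
- s = 50%: 7.3 points by Kaplan-Meier, 6.1 true; overstated by 1.1 (from unrounded values).
- s = 75%: 10.0 against 9.2; overstated by 0.8.

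**Step 4: MI or stroke.** With event hazard h and death hazard d over 24 months, the true incidence is h/(h + d) × (1 - exp(-(h + d))). Take an assumed Kaplan-Meier rate of 5%, so h = -ln(0.95) = 0.0513.
- Mortality 5%: true 4.88%, excess 0.1 points.
- Mortality 10%: true 4.75%, excess 0.3 points.
- Mortality 20%: true 4.49%, excess 0.5 points.

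Over Kaplan-Meier rates of 2-5% and mortality of 5-25%, the excess is about 0.1-0.7 points.

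**Step 5: comparison with sampling error.** The binomial standard error is sqrt(p(1 - p)/150).
- Placebo: p = 0.175 gives 3.1 points and p = 0.2625 gives 3.6 points, against a bias of 1.9 and 1.4.
- Arm difference: the 95% half-width is 7.9 points at s = 50% and 9.3 points at s = 75%, against a bias of 1.1 and 0.8.

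**The case against.** **The secondary endpoint could be a composite.** Section 3.6.2 opens by repeating the components of the primary endpoint and joins the list with *or*. It could mean one broader composite that includes death, and Kaplan-Meier is valid for that. This stands as a possibility. Three things favour separate endpoints: the word *composite*, used for the primary, is absent; reading the first two items as a unit would only restate the primary endpoint; and each event type has its own definition. The last is weak evidence, since a composite would need those definitions too.

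**Later sample sizes.** A reader might infer that inflated rates would pass straight into the next trial's sample size. The protocol does not support that. Section 5.1 sizes this trial on the primary composite only ("the event rate for primary outcomes was 35% at 24 months in the control group"), for which Kaplan-Meier is correct, and nothing says a later trial would be sized on a non-fatal event alone. What stands is narrower: absolute event rates are a declared product of this trial, and some of them would be too high.

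**Crude percentages may also be reported.** Section 5.2.3 gives counts and percentages for categorical data. With fixed 24-month follow-up and 5% assumed withdrawal, a crude proportion would be close to the true incidence. The protocol does not say that each endpoint will be tabulated this way, so this softens the point without removing it.

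**The bias is small, and the details could sit in a SAP.** The bias is below sampling error in an exploratory trial, and its size depends on a split the protocol does not give. Both are true. Competing-risk handling is often left to a SAP, but here the protocol assigns an estimator to all time-to-event endpoints without exception, so it has fixed the method rather than left it open.

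**Conclusion.** The point holds for heart-failure rehospitalization, non-fatal MI and non-fatal stroke when each is analysed on its own. The direction of the bias is certain whenever deaths precede the event; its size rests on the stated assumptions and is modest. It would be wrong to infer that the trial's main result is affected: the primary composite and all-cause death count death as an event, and a Cox hazard ratio with death censored keeps its meaning as a cause-specific hazard ratio. Only the absolute-risk curves for the non-fatal endpoints, and differences read from them, are overstated. A correction is worthwhile because the error is systematic, cheap to avoid, and falls on rates the trial says it will supply.

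**What to change.** In section 5.2.3, limit Kaplan-Meier to the primary composite, all-cause death and any other composite that includes death. For heart-failure rehospitalization, non-fatal MI and non-fatal stroke, specify Aalen-Johansen cumulative incidence curves with death as a competing event, and keep the Cox hazard ratios, labelled cause-specific. Section 3.6.2 should also state whether the secondary events are separate endpoints or a composite, since that decides which estimator applies.

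The cost is one or two sentences and a few lines of R. No new data are needed, because section 3.5.2 already has endpoint events recorded at visits and by telephone. The reported rates of the non-fatal endpoints will be slightly lower.

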3.3 Number of Cases and Grouping Method

The overall trial plans to enroll 300 patients who meet the inclusion criteria, and they will be randomly assigned to either the treatment group or the control group, with 150 patients in each group. This study is a prospective, multicenter, randomized, and controlled trial. It is planned to include 100 cases from our hospital, 100 cases from Affiliated Zhongshan Hospital of Dalian University, 50 cases from the First Affiliated Hospital of Sun Yat-sen University and 50 cases from Shanxi Cardiovascular Hospital.

Randomization: The randomization method employed in this study is block randomization. The statistician generated a random number table using computer software and conducted drug blinding based on it.

Blinding Procedure: Participants who are randomly assigned to the placebo group will also take capsules that are identical in appearance to those containing lipoic acid. Investigators at each center will be unaware of the difference between the two. Under normal circumstances, the blind will be maintained until all participants have completed the study and the database has been finally locked. Emergency unblinding may only occur when the participant's treatment status is required to determine special

emergency treatment. The date, time, and reason for unblinding will be recorded in the original documents and CRF (Case Report Form) tables.

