3.5.2 Follow-up Period

Patients underwent baseline visits on Day 0 post-randomization, followed by visits at Months 6, 12, and 24, totaling 4 on-site visits for efficacy, compliance, and safety assessments until study completion. The follow-up period lasted 24 months.

Visit 1 (Screening and Enrollment Period)

Inclusion and exclusion criteria

Informed consent signing

Past medical history and comorbidities

Comprehensive physical examination

Detailed documentation of medical history, comorbidities, treatment, concomitant medications, blood pressure, heart rate, weight measurement.

Cardiac function assessment (6-minute walk test: 6MWD)

Electrocardiogram (ECG)

Echocardiography

Laboratory tests: blood/urine/biochemical parameters, brain natriuretic peptide (BNP), coagulation function

Distribution of study medication

Instructions for the next follow-up visit date and brief physical examination

Visit 2 (Month 6 post-randomization), Visit 3 (Month 12 post-randomization), Visit 4 (Month 24 post-randomization)

Heart failure symptoms and signs

Comprehensive physical examination

Blood pressure, heart rate, weight measurement

Documentation of primary and secondary endpoint events

Adverse event recording

Cardiac function assessment (6MWD)

ECG

Echocardiography

Laboratory tests (blood/urine/biochemical parameters, BNP), coagulation function

Distribution/collection of study medication

Instructions for the next follow-up visit date or study termination

During months without on-site visits, researchers should contact patients via telephone to inquire about adverse events, endpoint events, and changes in concomitant medications, completing corresponding records.

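### The Cox model for the primary composite names no baseline covariate, so as written it forgoes a modest gain in power from variables the trial already records

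*Protocol*

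**What the plan says.** Protocol section 5.2.3 analyses the time-to-event endpoints as time to first event, and its whole model statement is "Cox proportional hazard models were used to estimate HR and 2-sided 95% CI". It names no covariate, stratum or centre term, and it does not call the model unadjusted. The next sentence gives LVEF and 6MWD a linear mixed model "with study centers included as random effects".

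The same section lists age, sex, smoking, medical history, "NYHA functional class, NT-proBNP levels, LVEF (whether \leq 30%), and whether the patient received triple therapy" as subgroup factors only. Section 3.5.2 schedules echocardiography, the 6-minute walk and "brain natriuretic peptide (BNP), coagulation function" at Visit 1. NYHA class and age are eligibility items in section 3.2.

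On allocation, section 3.3 says "The randomization method employed in this study is block randomization" and names no stratification factor. Four centres are planned: two of 100 patients, then "50 cases from the First Affiliated Hospital of Sun Yat-sen University and 50 cases from Shanxi Cardiovascular Hospital". The sample size in section 5.1 assumes that "the event rate for primary outcomes was 35% at 24 months in the control group" and that "the HR for the ALA group was estimated to be 0.60 and a withdrawal rate of 5% at 24 months in both groups". No gain from covariates is assumed.

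**The concern.** The paragraph does write model terms, but for two secondary measures and not for the endpoint on which the trial is sized. Eligibility runs from NYHA II to IV and takes any LVEF up to 50%, so baseline risk is likely to vary. No stated design feature balances that risk between arms. In a Cox model, adjusting for strong prognostic variables raises the power of the treatment test, and the candidates here need no new data. At stake is some power in a trial that expects only about 85 primary events. The sentence also leaves the choice of adjustment open, and a choice made after unblinding would be hard to defend.

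**Working it through.** **Inputs (Protocol 3.3, 5.1, 5.2.3).** 150 per arm, fixed 24 months, control risk 35%, HR 0.60, withdrawal 5%. Design alpha is two-sided 0.10 and analysis alpha is two-sided 0.05. Centres are 100/100/50/50. Prognostic strength is not given, so the SD of the baseline log-hazard score is an assumption and is varied.

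**Step 1: the plan's own figure.**
- ALA-arm risk = 1 − 0.65^0.60 = 22.8%.
- Events without loss = 150 × (0.350 + 0.228) = 86.7. With 5% exponential loss, 84.6.
- Schoenfeld power = Φ(√(D/4) × |ln 0.60| − z). With D = 84.6, √21.15 × 0.511 = 2.349.
- At alpha 0.10: Φ(2.349 − 1.645) = 75.9%. The stated 80% is not reproduced; it needs 95 events.
- At alpha 0.05: Φ(2.349 − 1.960) = 65.2%. A simulated unadjusted Cox model gives 64.8%.

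**Step 2: centre stratum alone.** In simulation (4,000 trials per setting, allocation balanced within centre), an assumed centre log-hazard SD of 0 moved power at 0.05 from 64.8% to 64.9%. An SD of 0.3 moved it from 65.1% to 65.9%. The Monte Carlo SE is about √(0.65 × 0.35 / 4000) = 0.75 points.

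**Step 3: baseline score added, HR 0.60 read as marginal.** The arm risks are held at 35% and 22.8%. The adjusted fit includes the score and centre strata. Centre SD is 0.2 where the score SD is above 0.

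| Score SD (assumed) | Unadjusted, 0.05 | Adjusted, 0.05 | Gain (points) | Conditional HR |
|---|---|---|---|---|
| 0 | 64.8% | 64.8% | 0 | 0.600 |
| 0.3 | 63.3% | 65.3% | 2.0 | 0.593 |
| 0.5 | 63.3% | 67.0% | 3.7 | 0.584 |
| 0.7 | 64.4% | 71.8% | 7.4 | 0.570 |
| 1.0 | 65.2% | 78.8% | 13.6 | 0.541 |

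**Step 4: HR 0.60 read as a patient-level (conditional) effect.** In 2,500 trials per setting without centre effects, power at 0.05 goes from 63% to 67% at SD 0.5, from 56% to 65% at 0.8, and from 50% to 64% at 1.0. The unadjusted HR drifts to 0.63 at SD 0.8 and 0.65 at SD 1.0. A run with centre SD 0.2 gave 59.1% to 64.5% at SD 0.7. The gains resemble those in step 3, but the unadjusted level falls.

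**Step 5: the adjustment as it would be used.** With four covariates plus centre strata (1,500 trials per setting), uninformative covariates gave 64.7% against 64.5%, so there is no material cost. Gains were about 1 to 2 points at SD 0.3, 2 to 4 at 0.5, and 7 to 9 at 0.7 to 0.8, under either reading of HR 0.60.

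**Step 6: capacity.** Treatment plus four covariates is five parameters: 84.6 / 5 = about 17 events per parameter.

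**The case against.** The strongest reply is that the protocol is silent rather than wrong. Covariates of a Cox model are often listed in the SAP, which is not at hand. A reader might infer that the protocol states a treatment-only model. It does not, and that part of the objection stands. What remains is that the sentence, followed as written, gives an unadjusted analysis, in a paragraph that specifies terms for a less important endpoint.

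It can also be said that centre in a linear mixed model creates no duty to put centre in a Cox model, and that no stratified allocation is stated which the analysis would have to follow. Both are correct. A reader might infer that leaving out centre loses power; step 2 shows under 1 point, about simulation error.

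A reader might further infer that mixed baseline risk drags planned power down towards 50%. That follows only if HR 0.60 is a patient-level effect. Section 5.1 gives group-level figures and mentions no covariates, so a marginal effect is the natural reading. Unadjusted power then stays at 63% to 65% throughout. The marginal HR is a legitimate target in its own right, not a biased one.

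Finally, the score in steps 3 and 4 is perfectly measured and correctly modelled, so those gains are best cases. The trial also calls itself exploratory and a pilot. These points limit the size and urgency of the issue; they do not remove it.

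**Conclusion.** The point holds as a missed improvement, not as an error in the document. With no term named beyond treatment, the primary Cox analysis forgoes precision from variables the trial already records. For an assumed score SD of 0.3 to 0.8, the gain is about 1 to 9 points of power at two-sided 0.05. The starting point is about 64% if HR 0.60 is marginal. If the covariates are uninformative, nothing material is gained or lost. Fixing the list before unblinding is worthwhile whatever the SD.

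It would be wrong to conclude that adjustment repairs the trial's power. Sizing at alpha 0.10 and testing at 0.05 costs 75.9 − 65.2 = about 11 points, and the stated 80% is not reproduced even at 0.10. Those are separate matters that adjustment leaves in place.

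**What to change.** Before unblinding, state in the protocol or SAP that the primary Cox model is adjusted for a short fixed set of baseline variables: LVEF, log natriuretic peptide standardised within assay, NYHA class (II vs III-IV) and age. Stratification by centre may be added for consistency with the LVEF and 6MWD model. Name the conditional HR as the target of the primary analysis, and report the unadjusted HR as supportive.

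The change is to wording only and needs no new data, but it is not quite free:
- The conditional HR lies somewhat further from 1 than the marginal one (0.593 to 0.570 for SD 0.3 to 0.7 at the same arm risks), so the two must be labelled and not interchanged.
- Section 3.2 accepts either BNP or NT-proBNP, Visit 1 lists BNP, and the subgroup list uses NT-proBNP. The wording must therefore say how the assays are combined and how missing baseline values are handled.

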3.1 Design

This is a multicenter, double-blind, randomized, placebo-controlled, parallel-group, exploratory trial.

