3.2 Population

Inclusion criteria: 1. Patients aged 18 years or older who had been diagnosed with acute myocardial infarction (AMI) for more than 30 days. The diagnosis of AMI was based on the Fourth Universal Definition of Myocardial Infarction, which encompassed clinical evidence of acute

myocardial ischemia and with detection of a rise and/or fall of cardiac troponin (cTn) values, with at least 1 value above the 99th percentile upper reference limit (URL) and at least 1 of the following: symptoms of myocardial ischemia; new ischemic electrocardiogram changes; development of pathological Q waves; imaging evidence of new loss of viable myocardium or new regional wall motion abnormality in a pattern consistent with an ischemic etiology, identification of a coronary thrombus by angiography; 2. Patients were diagnosed with chronic heart failure (NYHA class II-IV) with a documented LVEF \leq 50%. The diagnosis of chronic heart failure was based on the global definition[16]: Symptoms and signs of HF with elevated natriuretic peptides (BNP) (NTproBNP $>$ 600pg/ml or BNP \geq 150pg/ml; NT-proBNP \geq 400 pg/mL or BNP \geq 100 pg/mL, if patients were hospitalized for heart failure within 12 months; 3. The patients were clinically stable and had received optimal medical treatment with a fixed dosage for at least 4 weeks; 4. Patients were fully informed about this study and provided written informed consent.

Exclusion criteria: patients who were allergic to drugs of similar chemical classes (Vitamin B) as well as known or suspected contraindications to the study drugs; already used other investigational drugs at the time of enrollment, or within 30 days or over 5 half-lives of the drug prior to enrollment; with a history of intolerance to recommended target doses of ALA; have been diagnosed with acute decompensated HF (exacerbation of chronic HF manifested by signs and symptoms that may require intravenous therapy); with systolic blood pressure $<$ 100 mmHg; severe liver function abnormalities (alanine aminotransferase (ALT) or aspartate aminotransferase (AST) more than 3 times the upper limit of normal); an estimated glomerular filtration rate (eGFR) $<$ 30 mL/min/1.73m², as measured by the simplified MDRD

formula; a serum potassium > 5.2 mmol/L; were pregnant or planning to become pregnant.

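### Optional improvement, secondary endpoints only: the model for change in LVEF and 6MWD names centre but not the baseline value, which would usually sharpen the 24-month comparison

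*Protocol*

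**What the plan says.** Section 3.6.2 of the Protocol makes LVEF and 6MWD secondary endpoints: "The changes of LVEF and 6MWD were also assessed from baseline to 24 months". Section 5.2.3 gives the method, a linear mixed-effects model for "differences in changes of LVEF and 6MWD between the ALA group and the placebo group, with study centers included as random effects". It names no other model term, and no baseline covariate appears elsewhere in the Protocol.

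The baseline values will be on file. Section 3.5.2 lists "Cardiac function assessment (6-minute walk test: 6MWD" and echocardiography at Visit 1, and repeats both at months 6, 12 and 24.

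Section 3.2 bears on how widely the baseline values can spread. On LVEF it reads "Patients were diagnosed with chronic heart failure (NYHA class II-IV) with a documented LVEF" of no more than 50%. On stability it reads "The patients were clinically stable and had received optimal medical treatment with a fixed dosage for at least 4 weeks". The Protocol states no SD, correlation, expected difference or power for either measure.

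**The concern.** A change score subtracts the whole baseline value from the follow-up value. That is the best use of the baseline only when the regression slope of follow-up on baseline equals 1. At any other slope, part of the baseline variation stays in the change score as noise. A baseline covariate removes that noise by estimating the slope.

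Only efficiency is at stake. Randomisation keeps both analyses unbiased. The cost of leaving baseline out is a wider confidence interval for the two continuous endpoints, with the sample size fixed at 300. Naming the covariate in advance also removes a later choice between adjusted and unadjusted results.

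**Working it through.** The plan has no figure of its own to reproduce for these endpoints, so the check compares the two analyses directly.

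**Inputs from the Protocol**
- 300 patients (5.1), allocated 1:1 (3.5.1).
- "a withdrawal rate of 5% at 24 months in both groups" (5.1), which leaves 300 × 0.95 = 285. Deaths would reduce this further.
- Two-sided α of 0.05 (5.2.3).
- Four centres with 100, 100, 50 and 50 planned patients (3.3).
- Entry limit of 50% on LVEF (3.2).

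**Assumptions**
- Correlation r between baseline and month 24: mainly 0.5 to 0.8.
- SD ratio k = month-24 SD / baseline SD: 0.9 to 1.2.
- For LVEF, the 50% limit lies 0.5 or 1 SD above the mean of the uncapped distribution. The share v of baseline variance that remains is then 0.486 or 0.630. For 6MWD, v = 1.
- r and k refer to the uncapped distribution, and the baseline SD is set to 1.

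**Formulas**
- Variance of the change: (1 − rk)²v + k²(1 − r²)
- Variance after baseline adjustment: k²(1 − r²)
- Standard-error ratio: R = √[1 + (1 − rk)²v / (k²(1 − r²))]

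The two variances differ by (1 − rk)²v. This is never negative, and it is zero only when rk = 1. In large samples adjustment therefore cannot lose precision; its cost is one degree of freedom.

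**Numbers for k = 1, v = 1 (6MWD)**
- r = 0.5: 0.25 + 0.75 = 1.00 against 0.75, so R = √1.333 = 1.155
- r = 0.7: 0.09 + 0.51 = 0.60 against 0.51, so R = √1.176 = 1.085
- r = 0.8: 0.04 + 0.36 = 0.40 against 0.36, so R = √1.111 = 1.054

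**Example for LVEF, k = 1, r = 0.7**
- v = 0.630: R = √(1 + 0.09 × 0.630 / 0.51) = 1.054
- v = 0.486: R = √(1 + 0.09 × 0.486 / 0.51) = 1.042

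**Excess standard error of the unadjusted change**

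| Measure | k | r = 0.5 | r = 0.7 | r = 0.8 |
|---|---|---|---|---|
| 6MWD | 0.9 | 22.4% | 15.4% | 12.6% |
| 6MWD | 1.0 | 15.5% | 8.5% | 5.4% |
| 6MWD | 1.1 | 10.6% | 4.2% | 1.6% |
| 6MWD | 1.2 | 7.2% | 1.7% | 0.2% |
| LVEF | 0.9 | 11–15% | 8–10% | 6–8% |
| LVEF | 1.0 | 8–10% | 4–5% | 3% |
| LVEF | 1.1 | 5–7% | 2–3% | 1% |
| LVEF | 1.2 | 4–5% | 1% | 0.1% |

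Outside this range of r, at k = 1, the excess is 24% (6MWD) or 12–16% (LVEF) at r = 0.3. At r = 0.9 it is 2.6% or 1.3–1.6%.

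**Power.** The 80% used here is only a yardstick, since the Protocol claims no power for these endpoints. Where the adjusted analysis has 80% power, the unadjusted one has Φ(2.802/R − 1.960). For r = 0.5, 0.7 and 0.8:
- 6MWD, k = 1: 67.9%, 73.3%, 75.7%
- LVEF, k = 1: 72.1–73.9%, 75.7–76.7%, 77.3–77.9%
- 6MWD, k = 1.2: 74.4%, 78.6%, 79.9%

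**Detectable difference.** For 285 patients and 80% power this is 2.802 × √(4/285) × √variance = 0.332 × √variance, in baseline SDs. For 6MWD at k = 1, unadjusted against adjusted, it is 0.332 against 0.287 (r = 0.5), 0.257 against 0.237 (r = 0.7) and 0.210 against 0.199 (r = 0.8).

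**Simulation.** This used 4,000 runs per setting and 285 patients in four centres of the planned proportions, with centre as a fixed effect in place of a random one. At r = 0.5, 0.7 and 0.8 the empirical ratios were 1.161, 1.077 and 1.049 (k = 1, no cap) and 1.076, 1.013 and 0.998 (k = 1.2, no cap), in line with the formula. The type I error of the unadjusted comparison was 4.5% to 5.5% over 12 settings (Monte Carlo standard error 0.3 points), which is nominal.

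**The case against.** The strongest objection is that nothing here is wrong. The phrase in section 5.2.3 describes the random part of the model, and a baseline term would be a fixed effect. The sentence does not list the fixed effects or exclude any, and covariates for a secondary endpoint are ordinary SAP content. This stands, and it is why the point is an optional improvement and not an error. The Protocol does, however, fix the outcome (change), the model class and one adjustment term, so a better version of the stated method can be named.

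The design also limits the weight: "This is a multicenter, double-blind, randomized, placebo-controlled, parallel-group, exploratory trial". Section 5.1 says the trial is to "get the reference data on outcomes related to clinical events for the future RCT with large sample size". That aim concerns clinical events, so it lends the point no support.

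The size rests wholly on assumed values, and the power figures at k = 1 are not the most favourable to the plan. At k = 1.2 and r = 0.8 there is practically nothing to gain. The 6MWD figures may also be somewhat high, because limiting entry to stable NYHA II–IV patients may narrow the baseline spread. All of this stands.

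The point falls away if all four visits are modelled as responses with a common baseline mean, since that recovers the same precision. Finally, month-24 values lost through death may matter more than a few percent of standard error. That is a separate question.

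**Conclusion.** The point holds as a minor improvement to two secondary endpoints. The direction is certain: leaving baseline out cannot make the comparison more precise, apart from one degree of freedom. The amount is not known. With equal SDs and a correlation of 0.5 to 0.8, the unadjusted standard error is 5.4% to 15.5% too large for 6MWD and about 3% to 10% too large for LVEF, if the entry limit lies 0.5 to 1 SD above the uncapped mean. The excess is larger if the month-24 SD is below the baseline SD, and near zero when r times k is near 1. There is no bias and no loss of type I error control, and neither the primary endpoint nor the sample size is affected.

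**What to change.** Keep the centre effect and add one clause to section 5.2.3: the baseline value of LVEF (or of 6MWD) enters the model as a fixed covariate, and the estimate is the treatment difference in change at month 24. If the month 6 and month 12 values are also entered, add a patient random effect or an unstructured within-patient covariance. If the SAP already contains the baseline term, the clause simply brings the Protocol into line with it.

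The cost is one clause of wording and one degree of freedom, since Visit 1 already collects the data. The clause does not settle how month-24 values missing through death are handled.
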